### **10.8 Handling of Missing Data**

Reasonable efforts will be made to obtain complete data for all patients; however, missing observations will inevitably occur due to patients lost to follow-up or noncompliance with required assessments. The reasons for missing data will be documented and evaluated (e.g. patient is deceased, lost to follow up, missed visit, etc.). In addition, the distribution of prognostic factors between patients with data and those without data will be examined to evaluate any potential sources of bias. Any missing observations will be described in detail and evaluated for assessment of possible bias. The planned sensitivity analyses for the primary outcome in the primary analysis population (including a tipping point analysis which addresses the worst case scenario in which treatment group subjects with missing observations are considered failures and control group subjects with missing observations are considered successful) is described in further detail in the Statistical Analysis Plan (SAP).

### **10.9 Pooling of Site Data**

The homogeneity of safety and effectiveness results across study sites will be examined and if no significant heterogeneity is found, the results will be pooled. The justification for pooling is that all study sites will follow one Protocol, use the same device system (PINPOINT or SPY Elite), follow the same Instructions for Use and perform surgery in accordance with surgical guidelines from ASCRS. Additionally, frequent contact and monitoring of the sites will be performed to ensure that all Study sites are evaluating participants and recording Study results in a reliable and reproducible manner. It is not anticipated that any individual Study site will dominate the Study results. Therefore, it is believed that these procedures will help to ensure that the data from these Study sites can be combined and analyzed as if generated at a single site. Further explanation on poolability analyses, including testing baseline factors and the handling of significant site interactions, is described in the SAP.

## **11 ESTIMATED DURATION OF THE STUDY**

The expected study duration is approximately 2.5 years. The study is expected to start in the first half of 2015 and take approximately 24 months to complete enrollment.

## **12 STUDY ETHICAL CONSIDERATIONS**

### **12.1 Ethical Conduct of the Study**

The study will be conducted in accordance with US 21 CFR Part 812 and US 21 CFR Parts 50, 54, and 56. Any additional requirements imposed by the local Institutional Review Board/Ethics Committee/Research Ethics Board or regulatory agency will be followed as necessary.

## 12.2 Informed Consent

The informed consent forms used for the study must comply with applicable laws and regulations. An Investigator must explain the medical aspects of the study, including the nature of the study and procedure, orally and in writing, in such a manner that the subject is aware of potential benefits and risks. Other elements of the informed consent process may be delegated by the Investigator. Subjects must be informed about all aspects of the clinical study that are necessary to make the decision to participate in the clinical trial. Subjects must be informed that participation is voluntary and that they may withdraw from the study at any time, without prejudice. Documentation of the discussion and the date of informed consent must be recorded in the source documentation. Subjects must give informed consent in writing.

The informed consent process must be conducted, and the form must be signed, before the subject undergoes any screening procedures that are performed solely for the purpose of determining eligibility for the study.

## 12.3 Institutional Review Board, Ethics Committee, or Research Ethics Board (IRB)

The protocol, protocol amendments (as specified by the IRB), and the informed consent form for the proposed study, along with any other documents required by the center's IRB must be submitted by the Investigator to the center's duly constituted IRB for review and approval. The Investigator must also ensure that the IRB reviews the progress of the study on a regular basis and, if necessary, renews its approval of the study on an annual basis. A copy of each IRB approval letter must be forwarded to the Sponsor before the study is implemented. Documentation of subsequent reviews of the study must also be forwarded to the Sponsor.

## 13 ADMINISTRATIVE PROCEDURES

### 13.1 Sponsor's Responsibilities

#### 13.1.1 Public Disclosure of Clinical Trials

The Sponsor will submit information about this protocol to the appropriate web-based national clinical trial registry and results database in each applicable regulatory region where the study is conducted. This includes but is not limited to the US National Institute of Health ([www.clinicaltrials.gov](http://www.clinicaltrials.gov)). The Sponsor will update the information, including any changes to the study or recruitment status throughout the study.

#### 13.1.2 Study Supplies

The Sponsor will provide the PINPOINT Endoscopic Fluorescence Imaging System and if requested, the SPY Elite Intraoperative Imaging System along with sufficient quantities of PINPOINT Procedure Kits with Introducer and SPY PAQs.

#### 13.1.3 Investigator Training

##### 13.1.3.1 Study Initiation Visit

Study centers will have a study initiation meeting to ensure the research personnel understand the protocol, study requirements, and data capture processes. This training will take place prior to enrollment of the first subject at each study center.

#### 13.1.3.2 PINPOINT and SPY Elite System

Appropriate personnel at the study centers shall be required to participate in training on the procedural use of PINPOINT and SPY Elite as it relates to the conduct of this study (refer to Section 6.1 and Section 6.2).

#### 13.1.4 Ongoing Communication of Safety Information During the Study

The Sponsor will provide the Investigator with documentation of UADEs and reportable events/effects, from all study centers, reported to regulatory authorities during the conduct of the study. The Investigator must forward this documentation to the IRB, as described in Section 9.3.

The Sponsor will also notify the Investigator about any other safety findings that could affect the safety of subjects, affect the conduct of the study, or alter the IRB's opinion about continuation of the study.

#### 13.1.5 Study Monitoring

The conduct of the study will be monitored by representatives of the Sponsor to ensure compliance with the protocol, GCP and applicable regulations. A separate study specific Monitoring Plan will outline the monitoring procedures to be followed, the required access to source data and the extent of source verification planned.

#### 13.1.6 Records Retention

The Sponsor must retain all documentation pertaining to the study according to Novadaq standard operating procedures.

### **13.2 Investigator's Responsibilities**

#### 13.2.1 Reporting and Recording of Study Data

Data will be captured and compiled using procedures developed by the Sponsor or their representatives. All requested study data must be recorded clearly on the CRF and other study forms as required. An explanation should be provided for all missing data. Only individuals who are identified on the Study Signature and Delegation Log may enter or correct data in the CRF. Incomplete or inconsistent data on the CRFs will result in data queries that require resolution by the Investigator.

The protocol, informed consent form, protocol amendments, safety information, and other required documents must be submitted to the IRB in a timely manner, as described in Section 12.3.

#### 13.2.2 Source Documentation

The Investigator must maintain adequate and accurate source documents upon which CRFs for each subject are based. They are to be separate and distinct from CRFs, except for cases in which the Sponsor has predetermined that direct data entry into specified pages of the subject's CRF is appropriate. These records should include detailed notes on:

- The oral and written communication with the subject regarding the study treatment (including the risks and benefits of the study). The date of informed consent must be recorded in the source documentation.
- The subject's basic identifying information, such as demographics, that links the subject's source documents with the CRFs.
- All relevant observations and data on the condition of the subject throughout the study.
- The subject's exposure to PINPOINT and SPY Elite.
- All adverse events.

### 13.2.3 Study Devices

The Investigator is responsible for ensuring the PINPOINT system and SPY Elite system, including imaging agent, is controlled and is used or dispensed only to subjects enrolled in the study. Only Investigators identified on the Signature and Delegation Log may use PINPOINT and SPY Elite for the purposes of this study.

The Investigator shall keep records documenting the receipt, use, return and disposal of the study device and components.

The Investigator will ensure that PINPOINT and SPY Elite is returned and that any other study material will be returned to the Sponsor or disposed of according to the Sponsor's instructions on completion of the study.

### 13.2.4 Records Retention

The Investigator must ensure that clinical study records are retained according to national regulations, as documented in the clinical trial agreement entered into with the Sponsor in connection with this study.

Subject files and other source data must be kept for the maximum period of time permitted by the hospital, institution, or private practice. The Investigator must inform the Sponsor immediately if any documents are to be destroyed, to be transferred to a different facility, or to be transferred to a different owner.

## 13.3 Data and Safety Review

A Data and Safety Monitoring Committee (DSMC) has been established by the Study Sponsor to oversee the safety and other aspects of the study. The DSMC will also be responsible for reviewing the interim analysis conducted by an independent statistician in conjunction with the Study Sponsor and/or the Sponsor's Delegates and advising the Study Sponsor on determining the sample size of Stage 2. The DSMC consists of two independent board certified colorectal surgeons and an independent biostatistician. Ad-Hoc members may be appointed if specific expertise is needed. The role of the DSMC is to provide independent oversight and ensure that the study is conducted according to currently established safety and ethical standards. The Sponsor will oversee the provision of data to the DSMC. In general, it is anticipated that the DSMC meets twice a year. The DSMC reviews and evaluates all SAEs, UADEs and outcome measures and also receives a summary report for all ADEs and non-serious AEs. Unless specific action is required, the results of the analyses reviewed by the DSMC will not be shared

with site investigators. The DSMC will also develop rules for stopping the study. The Study Sponsor will distribute DSMC summary reports to collaborating clinical sites for submission to the sites' IRB. A separate DSMC Charter will define monitoring procedures and stopping rules.

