All subjects will be followed to monitor occurrence of adverse events (AE) and post-operative complications up to Week 8 (56 ±14 days) post-surgery. All subjects will have study specific follow-up visits on Day 1, date of discharge, Week 8 and the date of ileostomy closure (if applicable). Subjects with a discharge date later than Week 8, will be followed until discharge if the Investigator documents that the extended hospitalization is directly related to the surgical procedure or the PINPOINT and/or SPY Elite System. All subjects with a diverting ileostomy must have endoscopy and/or contrast enema of the anastomosis between 3 weeks post-surgery and the Week 8 visit (±14 days).

Subjects who present with a clinical suspicion of anastomotic leak during the study who do not clinically require an urgent reoperation will have a CT scan with PO and, if necessary, rectal contrast to confirm. A leak is considered confirmed if endoluminal contents (air, fluid, GI contents or contrast material) through the anastomosis is identified by imaging, drain output or at reoperation. The scans will be reviewed by an independent radiologist for confirmation. The presence of infection or abscess thought to be related to the anastomosis may be classified as an anastomotic leak at the surgeon's discretion even if it cannot be definitively identified as visualized during an operation or by contrast extravasation. All anastomotic leaks will be followed until resolution.

For patients with a diverting ileostomy, a leak may be identified by direct visualization of an anastomotic defect via sigmoidoscopy or by rectal contrast imaging, regardless of presence or absence of clinical symptoms.

All AE and post-operative complications occurring during the study period will be reported and graded according to the Clavien-Dindo system^20.

Analysis of anastomotic leak rate will be based on the occurrence of a leak according to the protocol definition at any time during the study up to Week 8.

This study is evaluating the utility of the PINPOINT or SPY Elite system only, and therefore the study protocol describes the requirements and use of these devices only.

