#### 5.1.1 Randomization Procedure

The study coordinator or a designee will log into the EDC system and be asked a series of questions verifying that the patient is eligible and that informed consent has been obtained prior to initiating the randomization process. Once the subject is under anaesthesia, the study coordinator will select the randomization envelope with the lowest randomization number from the neoadjuvant or non-neoadjuvant randomization box depending on if the subject has received prior neoadjuvant therapy or not. The study coordinator will then disclose the randomization assignment to the Investigator. The study coordinator will then write the subject's initials, date of birth, and date of randomization on the randomization card. A second study coordinator or designee will witness the randomization procedure and will sign and date the randomization card verifying that the randomization procedure was followed correctly. The randomization card will be maintained in the subject's file. As there is no ability for a sham comparison, the investigator cannot be blinded to the use of the PINPOINT or SPY Elite device. Patients will be blinded to their randomization assignment until after the procedure.

A subject is not randomized until a randomization envelope seal has been broken. The randomization procedure should not be initiated unless the EDC system confirms that a patient is eligible and verifies baseline information. If any deviations occur (errors such as misplacing envelopes), or if the randomization assignment is made incorrectly, the clinical site will be required to contact the Sponsor and await guidance on how to proceed.

If, at any time after randomization, the subject becomes ineligible or withdraws, the subject is still considered randomized. If an intraoperative decision is made to perform a procedure other than what was intended, the subject will be categorized with respect to the definitions outlined for the analysis populations (see the Statistical Methods Section 10.6).

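### Protocol section 13.3 does not keep the comparative interim leak results from the sponsor, so stage 2 is open to influence if the interim analysis is run

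*Protocol*

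**What the plan says.** **Protocol 13.3.** The DSMC reviews the "interim analysis conducted by an independent statistician in conjunction with the Study Sponsor" and/or its delegates. Its tasks include "advising the Study Sponsor on determining the sample size of Stage 2". On data flow: "The Sponsor will oversee the provision of data to the DSMC". The one restriction reads "Unless specific action is required, the results of the analyses reviewed by the DSMC will not be shared", and the sentence goes on to name site investigators only. A separate DSMC Charter is to cover monitoring procedures and stopping rules; 13.3 does not say that it governs sponsor access.

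**Protocol 10.4.** At 450 subjects the leak rates are compared one-sided. The trial stops for efficacy if p < 0.0169 and for futility if p ≥ 0.4. Otherwise conditional power (CP) at 800 is computed from the interim data. If CP is at least 0.5 and below 0.8, N is raised to reach 80% CP, with a cap of 1000. The section states that type I error is controlled.

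**Blinding and endpoint.** Section 5.1.1 says that "the investigator cannot be blinded to the use of the PINPOINT or SPY Elite device"; patients are blinded until after the procedure. Under section 3.1 an infection or abscess thought to be related to the anastomosis "may be classified as an anastomotic leak at the surgeon's discretion".

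**Sponsor's roles.** The sponsor trains surgeons (6.3.1) and monitors sites (13.1.5). The sponsor or its designee reviews data and issues queries (14).

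**SAP 3.1, 3.3 and 6.1.** The sample is everyone enrolled through 31 March 2017. The primary test uses one-sided 0.025. No interim analysis or stage 2 is described.

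**The concern.** The type I error statement in section 10.4 concerns the change in sample size. It takes for granted that the interim result does not alter how later subjects are operated on, followed or classified. When the party that runs the trial may know the leak rates by arm, that assumption rests on nothing the protocol states.

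The routes are ordinary ones: training of surgeons who join later, monitoring, the choice of data queries, and attention to borderline infections that an unblinded surgeon may or may not call a leak. At stake is whether a positive result in a pivotal trial can be defended against the charge that stage 2 was conducted with knowledge of stage 1.

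**Working it through.** **1. How 13.3 can be read.** Either the sponsor and/or its delegates take part in conducting the interim analysis, or they join the DSMC in reviewing it. Neither reading excludes the sponsor. No other section keeps by-arm interim results from it. Section 5.1 denies it the randomization schedules, which protects future assignments but not interim results.

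**2. Is the interim comparative?** Yes. The p-value and CP in section 10.4 cannot be computed without leak counts by arm.

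**3. The plan's own figures.** With t = 450/800 = 0.5625, Pocock-type spending gives 0.025 × ln(1 + (e − 1) × 0.5625) = 0.025 × ln(1.9665) = 0.0169, as stated. Solving the bivariate normal with correlation √0.5625 = 0.75 gives a final bound of z = 2.220 (one-sided p 0.0132; derived, not stated in the protocol). Power at 12.5% vs 6.25% with pooled variance is 81.6%, as stated.

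**4. How informative the interim is.** Under the observed trend, CP = Φ[(z₁/√t − 2.220)/√(1 − t)].
- CP = 0.5: z₁ = 0.75 × 2.220 = 1.665, one-sided p = 0.048.
- CP = 0.8: z₁ = 0.75 × (2.220 + 0.8416 × 0.6614) = 2.083, one-sided p = 0.019.

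**5. What a revised N reveals.** For N = 900, t = 0.5 and z₁ = 0.7071 × (2.220 + 0.8416 × 0.7071) = 1.991. At an assumed pooled leak rate of 9.375%, the difference is 1.991 × √(2 × 0.09375 × 0.90625/225) = 5.5 points (4.5 to 6.1 points for pooled rates of 6% to 12%). An N of 1000 says less, because the cap covers z₁ from 1.665 to 1.908.

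**6. Share of subjects exposed.**
- Outside the interim set: 350/800 = 44%; 550/1000 = 55%.
- Enrolled after the look, if accrual is uniform over 24 months (section 11) and does not pause: 800/24 ≈ 33 per month. Waiting 8 to 10 weeks (Week 8 visit, 56 days, to the end of its window, 70 days) adds about 61 to 77 subjects. That leaves 273 to 289 of 800 (34–36%), or 473 to 489 of 1000 (47–49%).

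The smaller figures apply to influence on the operation. Some subjects operated on during the wait could still have their leak status classified later, so the larger figures are the upper limit.

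**7. Illustration, not an estimate.** Assume no true effect, a 12.5% leak rate, N = 800, binding futility, and under-classification of PERFUSION-arm leaks among all 350 subjects outside the interim set. By simulation, if 10%, 20% or 30% of those leaks went unclassified, one-sided type I error would be about 3.3%, 4.6% or 6.9% instead of 2.5%. Nothing in the documents says that this would happen.

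**The case against.** **The interim may not exist.** The SAP plans no interim, so there may be no stage 2. This stands as a condition on the whole point. It does not remove it, because the protocol still specifies the interim.

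**The wording may be harmless.** Delegates alone would satisfy it, the phrase could mean operational support, and the Charter may contain a firewall. A reader might infer from 13.3 that the sponsor will certainly hold the by-arm results. The documents do not support that; they support only that the protocol does not prevent it.

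**Safeguards exist.** The independent radiologist is final on CT and contrast enema scans for suspected leaks (13.4), N follows a formula (10.4), and training comes before a surgeon's first enrollment or first use of the device (6.3.1). These narrow the routes. They do not reach leaks found at reoperation or by drain output, or discretionary calls without contrast extravasation.

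**The sponsor could work it out anyway.** Leaks are reported to it as SAEs within 24 hours (9.3, 9.4), PERFUSION-arm videos arrive under the subject number (8.5), and paper CRFs may go to it or its designee (14). This is correct. The wording of 13.3 therefore adds less exposure than it first appears to, and editing 13.3 alone would not be enough.

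**Conclusion.** The point holds as a gap in information control. Section 13.3 brings the sponsor and/or its delegates into the conduct or review of a comparative interim analysis, and restricts sharing only towards site investigators.

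A reader might go further and conclude that stage 2 was biased or that type I error is inflated. The documents show neither. The size of any bias cannot be derived from them, and the narrow p-value range of the promising zone measures how informative the look is, not how much harm follows.

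Up to 44% of 800 or 55% of 1000 subjects fall outside the interim set. About 34–36% or 47–49% would be enrolled after the look under uniform accrual over 24 months with no pause. All of this depends on the protocol's interim being run and on the Charter not already excluding the sponsor.

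**What to change.** - In 13.3, end the description of the interim analysis at the independent statistician and delete the words that attach the sponsor and its delegates.
- State that the independent statistician reports by-arm results only to the DSMC closed session.
- State that the sponsor receives only the recommendation: stop, continue, or the new enrollment target.
- Extend the no-sharing sentence to the sponsor and its delegates.
- Keep the detailed mapping from interim result to N in a restricted document.
- Bar sponsor trial staff from tabulating leaks by arm before database lock.
- Reconcile the protocol and SAP on whether there is an interim. If it has already been run, document who had access to the results.

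**Cost.** Wording in the protocol and Charter, plus an access rule for sponsor trial staff; the independent statistician and DSMC are already in place. Alpha, the 0.0169 bound, 81.6% power and the 450/800/1000 sizes do not change. The sponsor gives up sight of the interim rates. Disclosure is reduced but not eliminated, since some inference from a revised N or from SAE reports remains possible.

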#### **13.4 Independent CT/Contrast Enema Scan Assessment**

An independent Radiologist will review CT/contrast enema scans for all subjects who present with a clinical suspicion of anastomotic leak during the study. The independent Radiologist's assessment will be the final determination recorded for the study database. A separate IR Charter will define the image acquisition, data management and image analysis procedures.

